Contraceptive efficacy during extended duration of use of Mirena during years 6, 7 and 8 is expected to be high, as the lower release rate of other LNG IUS products (Skyla and LCS16) have been proven to provide high efficacy with a Pearl Index of less than 0.5 up to 3 years (11) and 5 years (9). Risks associated with contraceptive failure (i.e. risk of ectopic pregnancy, and risk to a pregnancy with Mirena in situ) are not expected to change during years 6, 7 and 8 with continued high contraceptive efficacy, which will be demonstrated in the proposed clinical study.

The bleeding profile during the extended use of the same device is expected to remain favorable and similar to that observed during the use up to 5 years. The incidence of infrequent bleeding or absence of bleeding increase with time in users of LNG IUS, while the incidence of prolonged and frequent bleeding decreases. Absence of bleeding is associated with high overall satisfaction and continuation rates in women using a second consecutive Mirena (12).

The study will also analyze the removal procedure after 8 years of use to confirm the usability of the product for the extended duration of use. No new risks are anticipated.

In summary, a positive benefit risk balance is anticipated during the extended use of Mirena for contraception up to 8 years.

4. Study objectives

Primary objective of the study is to assess the contraceptive efficacy of Mirena beyond 5 years up to 8 years of use.

Secondary objectives for the study are the assessment of menstrual blood loss (in women that had Mirena inserted for the indication heavy menstrual bleeding [HMB]) and safety.

[figure not shown]
Further objectives are the population pharmacokinetic evaluation of LNG plasma concentration data and evaluation of user satisfaction.

5. Study design

Design overview

This is a multi-center, uncontrolled, single group study to be conducted in the US only. Study design is presented below in [Figure 5—1](#).

Figure 5—1 Overview of the study design

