The efficacy and safety of Mirena for contraception and HMB has been proven in a large clinical development program for up to 5 years, while no company sponsored study data is currently available for use of Mirena beyond 5 years. New clinical data is therefore needed. The planned study will assess the contraceptive efficacy of Mirena during extended use beyond 5 years up to 8 years. In addition, approximately 10% of the total number of women in the study will have had Mirena prescribed for contraception and heavy menstrual bleeding; these subjects will form the HMB subgroup to show that the efficacy in terms of menstrual blood loss is maintained during extended use. This study design allows access for extended use of Mirena in women who have already been using Mirena close to the end of the currently approved maximum period of use and therefore an option for longer interval between the IUS placements in those women, who wish to continue use of Mirena for contraception or contraception and heavy menstrual bleeding (HMB) beyond 5 years.

End of study

The end of the study as a whole will be reached as soon as the last visit of the last subject (i.e. end of study phone call at 3 weeks after Mirena removal) has been reached in all centers.

Primary completion

The primary completion event for this study is the last patient last visit (LPLV).

The primary completion date for this study according to the FDA Amendment Act is specified in a separate document (not part of this study protocol).

6. Study population

This section was changed in Amendment 1, see Sections 15.1.1.2, 15.1.1.3, and 15.1.1.12.

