9.1 Tabular schedule of evaluations

This section was changed in Amendment 1, see Sections 15.1.1.1, 15.1.1.16, 15.1.1.24 and 15.1.1.25.

Table 9–1 presents the schedule of activities and evaluations for the study. The additional activities for the subjects in the HMB subgroup are displayed in Table 9–2.

Table 9–1 Schedule of activities and evaluations – amended

Period	Screening (0 to 6 mo)			Treatment Period (3 years; Mirena years 6 thru 8)						Pregnancy Follow-up (up to 12 mo)		
	Prescreening contact (optional)	Screening	Baseline						EOT ^a	EOS All subjects	3-mo contact ^b	12-mo contact ^c
Visit												
Visit number	☎/✉	1	2	3	4	5	6	7	8	☎	☎	☎
Timing		within 60 days	Day 1	6 mo ±14 d	12 mo ±14 d	18 mo ±14 d	24 mo ±14 d	30 mo ±14 d	36 mo -14 d	3 wks after EOT -3 d	3 mo after EOT -7 d/+14 d	12 mo after EOT +7 d
Duration of Mirena use		4 y 6 mo to 5 years	5 years ^d		6 years		7 years		8 years			
Urine pregnancy test ^g		X	X	X	X	X	X	X	X	X ^g		
Safety laboratory and urinalysis		X			X		X		X			
FSH		X										
Blood sample for PK ^h			X	X ⁱ	X ⁱ	X ⁱ	X ⁱ		X			
Concomitant medications		X	X	X	X	X	X	X	X			
Adverse events		X	X	X	X	X	X	X	X			
Continuing need for contraception				X	X	X	X	X	X			
Dispense home pregnancy test kits			X	X	X	X	X	X	X			
eDiary dispensed / collected			X						X			
Back-up contraception (if used; eDiary)			→	→	→	→	→	→	→			
Record uterine bleeding (daily, eDiary)			→	→	→	→	→	→	→			
Review of bleeding diary with subject				X	X	X	X	X	X			
Subject satisfaction with Mirena			X		X		X		X			
Mirena removal									X			
Mirena removal: ease and pain assessment									X			

Table 9–1 Schedule of activities and evaluations – amended

Period	Screening (0 to 6 mo)			Treatment Period (3 years; Mirena years 6 thru 8)						Pregnancy Follow-up (up to 12 mo)		
	Prescreening contact (optional)	Screening	Baseline						EOT ^a	EOS All subjects	3-mo contact ^b	12-mo contact ^c
Visit number		1	2	3	4	5	6	7	8			
Timing		within 60 days	Day 1	6 mo ±14 d	12 mo ±14 d	18 mo ±14 d	24 mo ±14 d	30 mo ±14 d	36 mo -14 d	3 wks after EOT -3 d	3 mo after EOT -7 d/+14 d	12 mo after EOT +7 d
Duration of Mirena use		4 y 6 mo to 5 years	5 years ^d		6 years		7 years		8 years			
Documentation of pregnancy/return to fertility										X	X	X

Please see next page for footnotes

Footnote Explanations:

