9.2 Visit description

General information

Timing of the visits

If not stated otherwise, the measures listed in the following sections will be performed by or under the supervision of a study site investigator.

There will be 8 scheduled study visits: screening visit (Visit 1), baseline visit (Visit 2), 5 visits during the treatment phase (Visit 3 to 7) and the end-of-treatment visit (EOT, Visit 8). The end-of-study visit (EOS) is a phone contact at 3 weeks after the EOT (all subjects).

In addition, there will be up to 2 follow-up contacts for post-treatment pregnancy tracking. 3-month follow-up contact is for subjects who prematurely discontinued study treatment unless the reason for discontinuation is “pregnancy”, “death”, or “withdrawal by subject” where the subject has withdrawn main consent during study conduct and wishes to stop future contact with the site. For subjects that had withdrawn consent during study, but consented to post study participation follow-up, will be contacted. If subjects could not be contacted at 3 months, they will be considered “Lost to Follow-up” for post-study pregnancy tracking. 12-month contact is for subjects that prematurely discontinued treatment due to ‘Wish for pregnancy’. If a subject was not pregnant at 3-month contact but subject no longer wished to become pregnant, a 12-month contact is not required. If subject was “Lost to Follow-up” at 3 months, a 12-month contact is required. For details, see Section 9.4.1.2.

The screening period can start when the subject has had the Mirena in place for 4 years and 6 months. Screening period is up to 6 months. Screening activities should be completed within 60 days after signing the informed consent. The baseline visit (Visit 2) should take place 14 to 0 days before the end of Year 5 of Mirena use.

The timing of the visits is based on the date of the baseline visit. Treatment period starts at the baseline visit (Visit 2, defined as Study Day 1).

The following visit windows are allowed:

- Visits 3 to 7 (during treatment) should be performed ± 2 weeks of the scheduled day.
- Visit 8 (EOT) should be performed at the earliest 2 weeks before the scheduled day and not later.
- Follow-up contact (EOS) should take place 3 weeks after the EOT (-3 day window allowed).

Unscheduled visits

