- Perform pelvic examination to visualize Mirena removal threads (Section 9.6.3.8)
- Perform urine pregnancy test (Section 9.6.3.4)
- Interview for the following:
 - Concomitant medications (Section 8.1)
 - AEs (Section 9.6.1)
 - Continuing need for contraception (Section 9.7.1)
- Dispense home pregnancy kits with instructions (Section 9.6.3.4)
- Review completed (monthly) eDiary, including information on uterine bleeding and back-up contraception.
- Dispense alkaline hematin kit with instructions for subjects in HMB group.

Discuss the contraceptive options available after the study treatment with the subject (see Section 8.2).

9.2.9 36-month visit, EOT – Visit 8 (End of Year 8 of Mirena use)

This section was changed in Amendment 1, see Section 15.1.1.17.

The following procedures and assessments will be done:

- Assess vital signs and weight (Section 9.6.3.1)
- Perform general physical examination (Section 9.6.3.2)
- Perform gynecological examination (with **breast palpation**; Section 9.6.3.3)
- Perform pelvic examination to visualize Mirena removal threads (Section 9.6.3.8)
- Obtain cervical smear (Section 9.6.3.5)
- Perform urine pregnancy test (Section 9.6.3.4)
- Perform safety laboratory test and urinalysis (Section 9.6.3.7)
- Blood sample for PK (**all subjects**) (Section 9.5.1)
- Interview for the following:
 - Concomitant medications (Section 8.1)
 - AEs (Section 9.6.1)
 - Continuing need for contraception (Section 9.7.1)
- Dispense home pregnancy kits with instructions (Section 9.6.3.4)
- Review completed (monthly) eDiary, including information on uterine bleeding and back-up contraception.
- Collect eDiary device (Section 9.7.1)
- Subject satisfaction with Mirena (Section 9.7.4)
- Remove the Mirena (Section 9.7.3)
- Complete Mirena removal ease (investigator) and pain (subject) assessment

9.2.10 3-week follow-up call (EOS)

All subjects will be contacted 3 weeks after EOT (i.e. after Mirena removal) to collect information on any pregnancy detected shortly after the end of study treatment, see Section 9.4.1.

9.2.11 3-month follow-up contact for post-study pregnancies

This section was changed in Amendment 1, see Section 15.1.1.6.

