9.6.1.3 Assessments and documentation of adverse events

The investigator has to record on the respective eCRF pages all adverse events occurring in the period between the signing of the informed consent and the end of study; after the end of the study there is no requirement to actively collect AEs including deaths. The type of information that should be assessed and recorded by the investigator for each AE is listed in Section 9.6.1.2.

“Death” should not be recorded as an AE on the AE page. Instead, “death” is the outcome of underlying AE(s).

For all serious adverse events (SAEs) the sponsor has to carry out a separate assessment for expectedness, seriousness and causal relationship to study drug.

The following events should **not be reported as AEs/SAEs**, unless (i) they are specifically considered as such by the investigator, according to the following conditions, or (ii) they lead to withdrawal of a subject from the study. This is to avoid redundancy and/or inconsistent reporting of AEs as these data may already be recorded in the CRF or subject’s eDiary.

- **Ovarian cysts:** An ovarian cyst should only be reported as an AE if it is felt to be non-physiologic (at the discretion of the investigator). Ultrasound examinations will not be routinely scheduled as part of this study but may be performed by the investigator if thought to be necessary to evaluate symptoms of an ovarian cyst or other pelvic pathology. If an ovarian cyst is diagnosed, follow-up should be in accordance with the investigator’s standard practice.

- **Findings on the bleeding diary:** Uterine bleeding (including intracyclic bleeding and absence of bleeding) should be recorded as an AE only if:
 - it leads to study discontinuation
 - it leads to therapeutic or diagnostic procedures
 - it is regarded as SAE
 - it shows a clinically significant worsening during the study that, in the judgment of the investigator, is not consistent with the expected clinical course, or are specifically reported as AEs by the subject.

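### The AE recording period runs to the call 3 weeks after Mirena removal, but the last scheduled AE inquiry is at the removal visit, so AEs in those 18 to 21 days are in scope but not solicited.

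*Protocol*

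**What the plan says.** Protocol 9.6.1.3 sets the AE period: the investigator records "all adverse events occurring in the period between the signing of the informed consent and the end of study". It then adds that "after the end of the study there is no requirement to actively collect AEs including deaths", which implies that active collection is expected up to that point. Section 9.6.1.4 ties SAE reporting to the same observation period.

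Section 5 ends the study as a whole at the last woman's "end of study phone call at 3 weeks after Mirena removal". Section 9.2 calls the same contact the end-of-study (EOS) visit, holds it for all subjects, and allows it up to 3 days early but not late.

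In Table 9-1 the row "Adverse events" is marked at Visits 1 to 8 and is blank at EOS, as is the concomitant-medication row. Section 9.2.10 says the EOS call is made "to collect information on any pregnancy detected shortly after the end of study treatment"; Section 5 describes it the same way. Mirena is removed at Visit 8 (9.2.9).

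On the analysis side, SAP 6.4 defines treatment-emergent AEs as those in the extension treatment period, which SAP Section 3 describes as the 3 years following Day 1 of Year 6. The working rule in SAP 4.7 gives only a lower bound: onset on Day 1 of Year 6 or later. Year 8 is likewise open at the upper end and takes in AEs at the start of Year 9.

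**The concern.** A site that follows the schedule of activities exactly would never ask a woman about AEs after the visit at which her device came out, although the protocol counts the next 3 weeks as part of the AE and SAE period. Nothing else routinely covers that interval: the bleeding diary stops at removal (9.6.3.12) and the device that holds it is collected at Visit 8 (9.2.9). Section 8.1 requires all medication taken during the study to be recorded, but that row stops at Visit 8 too, so treatment of a post-removal event could also be missed.

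What is at stake is the meaning of an empty or thin post-removal record. If few events appear after removal, the reader of the safety tables cannot tell whether few occurred or whether the question was not put. Events that do come to light may enter the treatment-emergent tables under the SAP 4.7 rule without being distinguishable from events on treatment. The Pearl Index, the sample size and the heavy menstrual bleeding endpoint are not affected.

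**Working it through.** The check is mainly textual. The documents give no figure for post-removal events, so there is none to reproduce.

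**Provisions side by side**

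| Item | Source | Runs to |
|---|---|---|
| Duty to record AEs | Protocol 9.6.1.3 | End of study |
| Duty to report SAEs | Protocol 9.6.1.4 | Same period |
| End of study | Protocol 5 and 9.2 | Call 3 weeks after removal |
| Scheduled AE inquiry | Protocol Table 9-1; visit lists 9.2.2 to 9.2.9 | Visit 8 (removal) |
| Scheduled medication inquiry | Protocol Table 9-1 | Visit 8 (removal) |
| Purpose of the EOS call | Protocol 5 and 9.2.10 | Pregnancy only |

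The end of study in 9.6.1.3 might mean the individual woman's EOS contact or the close of the whole study. Either falls after her Visit 8, so the mismatch stands on both readings.

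The blank at EOS is not a table-extraction fault. The AE row carries eight marks, for eight visits. The urine pregnancy test row carries a ninth, at EOS, and pregnancy documentation is marked there as well.

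**Length and size of the unsolicited window**

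Inputs:
- Interval from removal to call: 21 days, or 18 at the early edge of the window (21 − 3) (Protocol 9.2).
- Women targeted to complete treatment: 200 (Protocol 5 and 10.4).
- Women entering treatment: 360 (Protocol 5 and 10.4).
- One woman-year: 365 days (SAP 4.7).

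Formula: woman-years = women × days / 365.

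- Completers, 21 days each: 200 × 21 / 365 = 11.5.
- All 360, 18 days each: 360 × 18 / 365 = 17.8.
- All 360, 21 days each: 360 × 21 / 365 = 20.7.

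The figures for 360 are upper limits. The other 160 women (360 − 200) include early removals, and may include total expulsions and losses to follow-up with no removal in the study or no EOS call.

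**How the SAP would count such events**

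On the SAP 4.7 rule, any AE with onset on or after Day 1 of Year 6 is treatment-emergent, before or after removal. On the SAP 6.4 definition it must fall in the extension treatment period, so a completer's event in early Year 9 would fall outside. By contrast, the SAP does limit other data at removal: bleeding diary data after expulsion or removal are excluded (6.4.3), and LNG and SHBG concentrations after it are only listed (6.3.1). No such rule is given for AEs.

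**The case against.** The strongest reply is that the duty to record is intact. Section 9.6.1.3 binds the investigator to end of study, SAEs must be reported within 24 hours of awareness, sites are trained on SAE reporting, and every woman is telephoned. Whether the eCRF page for the call prompts for AEs cannot be seen from these documents. All of this stands. It limits the point to solicitation, but it does not remove it: awareness depends on being told, and neither document tells the site to ask.

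Part of the likely harm is also covered. Ease and pain of removal are recorded at Visit 8 (9.7.3). Technical difficulties at removal trigger a product complaint with return of the device (7.6). Pregnancy is asked about on the call, and abnormal pregnancy outcomes are reported as SAEs (9.4.1.1). This stands as well. What remains is events that arise after the woman has left Visit 8.

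Several stronger readings are tempting and are not supported:

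- A reader might infer that post-removal harms of an 8-year-old device are lost altogether. They are not: volunteered events must be recorded. The gap also affects every removal, including early ones, and not only devices worn for 8 years.
- A reader might multiply 360 removals by an assumed event rate to get a count of missed events. The documents give no such rate, and only about 200 women are expected to reach 8 years.
- A reader might take the statement in Section 3, "The study will also analyze the removal procedure after 8 years of use to confirm the usability of the product", to mean that post-removal AEs carry that aim. It concerns the removal procedure, which the Visit 8 ease and pain assessments address.
- A reader might take the SAP's inclusion of AEs at the start of Year 9 as proof that post-removal time was the target. The SAP gives no such reason. The exposure tables (Protocol Table 10-1, SAP Table 6-1) have a row for women continuing into a ninth year, which would explain it as well.
- A reader might rely on the AE interview being listed ahead of removal in 9.2.9. That list is not stated to be a sequence, and the point does not need it.

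**Conclusion.** The concern holds as an inconsistency within the protocol. The AE and SAE period extends 18 to 21 days beyond removal, while the schedule and the stated content of the EOS call provide no AE or medication inquiry in that time. A site working strictly to the schedule would under-ascertain events in a window that the protocol itself declares in scope.

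The size is about 11.5 woman-years for the 200 targeted completers, assuming each is called at day 21, and no more than 17.8 to 20.7 woman-years if all 360 women have a removal and a call. The number of events that would go unreported, and any difference between sites, cannot be derived from the documents. The SAP side is a secondary ambiguity: the working rule for treatment-emergent AEs has no upper bound, although the main definition refers to the extension treatment period.

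This is worth correcting because the remedy is cheap and improves safety ascertainment. It does not bear on the efficacy conclusions.

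**What to change.** 1. In Protocol Table 9-1, mark adverse events and concomitant medications at the EOS contact.
2. In Protocol 9.2.10, state that the 3-week call also asks about new or ongoing AEs and SAEs since removal, for women who discontinued early as well as for completers. Align the description of the call in Section 5.
3. In SAP 4.7 and 6.4.2, flag AEs with onset after the stop date of study drug administration, so that they can be shown separately. SAP 4.7 already defines that date, so no new data are needed for the flag. State whether flagged events also count in the treatment-emergent tables.

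If the sponsor instead means AE collection to stop at the end-of-treatment visit, 9.6.1.3 should say so. That would also remove the contradiction, but it would give up the post-removal information.

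The cost is one added question in a call already planned for all subjects, a small eCRF and protocol change, and slightly more reported AEs. Sample size, power and the confidence level are unchanged.

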9.6.1.4 Reporting of serious adverse events

The definition of serious adverse events (SAEs) is given in Section 9.6.1.1. Each SAE must be followed up until resolution or stabilization by submission of updated reports to the designated recipient.

Investigator's notification of the sponsor

All investigators will be thoroughly instructed and trained on all relevant aspects of the investigator's reporting obligations for SAEs. This information, including all relevant contact details, is summarized in the investigator site file. This information will be updated as needed.

The investigator must report immediately (within 24 hours of the investigator's awareness) all SAEs occurring during the observation period defined in Section 9.6.1.3 to the recipient detailed in the instructions for SAE reporting included in the Investigator File. For this, an AE page in the CRF as well as the complementary pages provided in the Investigator File must be completed for each SAE.

SAEs occurring after the protocol-defined observation period will be processed by the sponsor according to all applicable regulations.

Notification of the IECs / IRBs

Notification of the IECs / IRBs about all relevant events (e.g. SAEs, suspected, unexpected, serious adverse reactions [SUSARs]) will be performed by the sponsor and/or by the investigator according to all applicable regulations.

Notification of the authorities

The processing and reporting of all relevant events (e.g. SAEs, SUSARs) to the authorities will be done by the sponsor according to all applicable regulations.

Sponsor's notification of the investigational site

The sponsor will inform all investigational sites about reported relevant events (e.g. SUSARs) according to all applicable regulations.

9.6.1.5 Expected adverse events

For this study, the applicable reference document is the most current version of the investigator's brochure (IB).

Overview listings of frequent events that have occurred so far in the clinical development are shown in the current IB. If relevant new safety information is identified, the information will be integrated into an update of the IB and distributed to all participating sites.

The expectedness of AEs will be determined by the sponsor according to the applicable reference document and according to all local regulations.

